6 INTERIM ANALYSES

No interim analysis is planned.

7 CHANGES IN THE PLANNED ANALYSES

The sponsor has decided to terminate this study. With 22 subjects randomized, which represents for 35% of the planned number, only descriptive statistics for primary, secondary, and selected exploratory endpoints will be provided. Subgroup analysis will be limited to seizure type, while sensitivity analysis will not be conducted.

Given the limited PK data, we will only provide summary statistics for plasma concentrations of lorcaserin. We will not derive steady-state PK parameters such as C_{max} and AUC, nor to explore relationships between exposure to lorcaserin and selected efficacy and safety endpoints.

8 DEFINITIONS AND CONVENTIONS FOR DATA HANDLING

8.1 Efficacy: Seizure Frequency per 28 Days

Seizure frequency for convulsive seizures, total seizures, non-convulsive seizures, and per seizure type, will be based on number of seizures per 28 days, calculated during the Baseline Period and Treatment Period, as the number of seizures during each respective period divided by the number of non-missing days during each respective period, multiplied by 28.

Eisai Final 4.0 Confidential Page 21 of 30

Baseline Period Seizure Frequency: number of seizures during the screening period to the date prior to randomization, divided by the number of non-missing days, multiplied by 28.

Treatment Period Seizure Frequency: number of seizures from the date of randomization to the end of the treatment period divided by the number of non-missing days, multiplied by 28.

Endpoint Definitions:

Percent Change from Baseline = 100 * (Treatment Period – Baseline Period) / Baseline Period

For the rank ANCOVA models the ranks of Baseline Period Seizure Frequency and the ranks of Percent Change from Baseline will be used in the analyses.

```
50% Responders = 1 if percent change from baseline ≤ -50%
0 otherwise
```

Seizure freedom for convulsive seizures, non-convulsive seizures, and total seizures, will be defined two ways; 1) counting seizures only and not counting clusters and 2) counting both seizures and clusters

```
Seizure-freedom = 1 if percent change from baseline = -100%
0 otherwise
```

Convulsive seizures: The sum of seizure frequencies of hemiclonic, tonic, clonic, tonic-atonic, generalized tonic-clonic, and focal with clearly observable motor signs.

Non-convulsive seizures: The sum of all other seizure frequencies not listed under convulsive seizures.

Total seizures: The sum of seizure frequencies for all seizure types.

S-curve plots (percent change from baseline on the x-axis and cumulative proportion on the y-axis) both treatment groups, will be provided for convulsive seizures, non-convulsive seizures and total seizures.

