9.3.1 Inclusion Criteria

Subjects must meet all of the following criteria to be included in this study:

1. Male or female, age ≥ 2 years at the time of informed consent (or assent)
2. Confirmed diagnosis of epilepsy with Dravet syndrome per Recommendations from a North American Consensus Panel (2017)
3. Has had at least 4 convulsive seizures during the 4 weeks of the Prerandomization Phase
4. Currently treated with at least 1 AED and the doses of all AEDs must be stable for at least 4 weeks before Screening, and be expected to remain stable throughout the study.
5. If vagal nerve stimulator, responsive neurostimulator, or deep brain stimulator is used, it must be implanted at least 5 months before Screening, parameters must be stable for at least 4 weeks before Screening, and be expected to remain stable throughout the study
6. If a ketogenic diet is followed, it must be stable for at least 4 weeks before Screening and be expected to remain stable throughout the study

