5.3.3 Examination of Subgroups

The primary endpoint and key secondary endpoint will be summarized using descriptive statistics by each subgroup listed below. No hypothesis testing will be performed in the subgroup analyses.

- Age group (≥ 2 to ≤ 12 yrs, ≥ 12 yrs)
- Sex (male and female)
- Race (white, black, Asian, and other)
- Region (US and Canada, India, and China/Brazil)
- Weight Strata (10 to \leq 20 kg, 20 to \leq 40 kg, and \geq 40 kg)
- Fenfluramine strata (yes, no)
- Prior to drug interruption, during drug interruption and after drug interruption
- Seizure types

Additional subgroup analyses may also be conducted, if deemed appropriate.

Eisai Final 4.0 Confidential Page 13 of 30

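### SAP 8.1 codes a subject with no non-convulsive seizures in either period as not seizure-free, while the non-convulsive S-curve cannot plot that subject

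*SAP*

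**What the plan says.** SAP 8.1 computes seizure frequency per 28 days for the Baseline and Treatment Periods and then defines "Percent Change from Baseline = 100 * (Treatment Period – Baseline Period) / Baseline Period". The freedom flag is built on that result: "Seizure-freedom = 1 if percent change from baseline = -100" per cent, and 0 in all other cases. The scope is explicit: "Seizure freedom for convulsive seizures, non-convulsive seizures, and total seizures, will be defined two ways" (with and without clusters). The same section asks for S-curves with percent change on the x-axis, and these "will be provided for convulsive seizures, non-convulsive seizures and total seizures". Non-convulsive seizures are every type outside the convulsive list.

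Protocol 9.3.1 sets one baseline count for entry: "Has had at least 4 convulsive seizures during the 4 weeks of the Prerandomization Phase". It sets no minimum for non-convulsive seizures.

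SAP 7, written after the decision to terminate with 22 subjects randomized, says that "only descriptive statistics for primary, secondary, and selected exploratory endpoints will be provided".

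**The concern.** The divisor in the percent-change formula is the baseline frequency, and SAP 8.1 does not say what happens when it is zero. For convulsive and total seizures this does no harm, because entry rules out a zero baseline. For non-convulsive seizures a zero baseline is possible, and the flag is still defined for them.

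The instruction to code every other case as 0 turns this from a missing detail into a rule that gives a wrong answer. A subject who never had a non-convulsive seizure, and had none on treatment, is counted as not free of them. The S-curve in the same section needs a percent change for each plotted subject and has none for this one. A reader who compares the reported freedom rate with the height of the curve at −100% could see two different figures for the same quantity.

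**Working it through.** The plan states no figure on this point, so there is none to reproduce. The check applies the SAP 8.1 rules as written and then sizes the disagreement on assumed counts.

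**Step 1: apply the rules.** Percent change = 100 × (T − B)/B, with B the baseline and T the Treatment Period frequency. The flag is 1 if the result is −100%, otherwise 0.

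| Baseline → treatment | Percent change | Freedom flag | Point on S-curve |
|---|---|---|---|
| 0 → 0 | 0/0, undefined | 0 | none |
| 0 → 2 | 200/0, undefined | 0 | none |
| 4 → 0 | −100% | 1 | yes |
| 4 → 2 | −50% | 0 | yes |
| 4 → 8 | +100% | 0 | yes |

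The first row is the fault: no seizures on treatment, flag 0, no plotted point. In the second row the flag is right, but the curve again omits the subject.

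**Step 2: where a zero baseline can occur.** An eligible subject has at least 4 convulsive seizures at baseline, so the convulsive baseline is above zero. The total includes the convulsive seizures, so it is above zero too. Nothing keeps the non-convulsive baseline above zero.

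**Step 3: size.** Inputs:
- 22 randomized (SAP 7), 1:1 allocation (SAP 3.2). The actual split is not stated; 22/2 = 11 per arm is assumed.
- k = subjects in an arm with no non-convulsive seizures in either period (assumed).
- f = other subjects in that arm who go from a positive baseline to none (assumed).
- No subject follows the 0 → 2 pattern (assumed).

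Flag rate over all 11 = f/11. S-curve at −100% = f/(11 − k). For k = 1 the gap is f/10 − f/11 = f/110.

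| k | f = 1: flag, curve, gap | f = 2: flag, curve, gap |
|---|---|---|
| 1 | 9.1%, 10.0%, 0.9 points | 18.2%, 20.0%, 1.8 points |
| 3 | 9.1%, 12.5%, 3.4 points | 18.2%, 25.0%, 6.8 points |
| 5 | 9.1%, 16.7%, 7.6 points | 18.2%, 33.3%, 15.2 points |

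The documents give no prevalence of non-convulsive seizures, so no row is known to apply. The last row needs nearly half an arm to have no such seizures at all.

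**Step 4: after the fix.** With both outputs restricted to B > 0, each equals f/(11 − k) and the gap is zero.

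**The case against.** The strongest reply is that an undefined value makes everything derived from it missing. The subject then leaves both outputs and the denominators agree. That is a sensible convention and a programmer may well follow it. It is not what the flag definition says, however, since that definition sends every case other than −100% to 0. A third convention, counting everyone with no seizures on treatment, is also possible: with k = 1 and f = 2 it gives 3/11 = 27.3%, against 18.2% and 20.0%. The choice needs to be written down.

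The second reply is that the rule may exist elsewhere. SAP 9 puts derivation rules in separate documents, SAP 11 puts table and graph shells in another, and the exploratory sections are not visible. This stands: only the visible text can be faulted.

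The third reply is that little depends on the flag. The freedom endpoint in SAP 5.1.3 is convulsive only, SAP 5.4.3 plans no other efficacy analyses, and SAP 7 keeps only selected exploratory endpoints, descriptively. This also stands, and it limits the weight of the point.

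A reader might go further and infer that the one retained subgroup analysis is affected, because SAP 7 says "Subgroup analysis will be limited to seizure type". The documents do not support that. Under SAP 5.3.3, "The primary endpoint and key secondary endpoint will be summarized using descriptive statistics by each subgroup listed below", and SAP 5.1.1 and 5.1.2 define both of those endpoints on convulsive seizures, whose baseline cannot be zero in an eligible subject. A zero baseline would arise there only if the subgroup label were read as creating new per-type endpoints. Per-type percent change is planned elsewhere (protocol 9.7.1.6.1 and Appendix 2), and the formula has no value for a subject without that type at baseline. But SAP 8.1 defines no freedom flag by individual type, so no wrong coding follows there.

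**Conclusion.** The point holds as a minor one. Followed as written, SAP 8.1 codes a subject with no non-convulsive seizures in either period as not seizure-free and leaves that subject off the non-convulsive S-curve. It does not touch the primary, key secondary, convulsive-freedom or total-seizure results for eligible subjects.

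The size is unknown. With 11 per arm and 1 or 2 others becoming free, one such subject gives a gap of about 0.9 or 1.8 points. The larger gaps in the table should not be read as expected effects, because they rest on counts that nothing in the documents supports. The conclusion also assumes that non-convulsive freedom is reported at all after termination, and that no zero-baseline rule stands in the specifications, the shells or the redacted text.

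**What to change.** In SAP 8.1, add a condition for non-convulsive seizures, and for any per-type percent change that is reported:
- compute percent change, the S-curve and (for non-convulsive seizures) the freedom flag only in subjects whose baseline frequency for that category is above zero;
- set the freedom flag to missing, not 0, for subjects with a zero baseline;
- show by arm the number of subjects with a baseline above zero.

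If a rule already exists in another document or a redacted section, a cross-reference from SAP 8.1 is enough. SAP 5.3.3 needs no change. Nor does freedom need redefining as no seizures on treatment: once the baseline is above zero, that is the same as a percent change of −100%.

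The cost is a sentence or two and one added n per table. The downside is smaller denominators for these descriptive summaries.

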3.2 Overall Study Design and Plan

This is a multicenter, multiple-dose, randomized, double-blind, placebo-controlled, parallel-group adjunctive therapy study in subjects with Dravet syndrome. The study is planned to be conducted in US, Canada, India, and China or Brazil (to be determined). The study will consist of a Core Study and open-label Extension Phase.

The Core Study will include a Prerandomization and a Randomization Phase.

The Prerandomization Phase will include a Screening/Baseline Period (4 weeks), during which the subjects will be assessed for eligibility.

Once the Screening and Baseline procedures have been completed and eligibility has been established, the subjects will be randomized and begin treatment in the Randomization Phase. Approximately 62 subjects will be randomized to 1 of 2 treatment groups in a ratio of 1:1 and will receive lorcaserin or placebo for 14 weeks. The randomization will be centralized and stratified by previous treatment with fenfluramine (yes, no) and by weight categories (10 to <20 kg, 20 to <40 kg, and ≥40 kg). The stratification factors will be balanced between treatment groups using restricted randomization method proposed by Pocock and Simon (1975).

The Randomization Phase will consist of 2 periods: Treatment Period (14 weeks) and Follow-up Period (4 weeks).

During the Treatment Period, all subjects will take study drug twice daily (BID) based on weight category at randomization, as described in Section 9.4.1 of the protocol.

For lower weight categories, during the first 2 weeks of Treatment Period, the dose may be increased (not earlier than after 1 week of treatment) by 1 dose level at a visit. If the dose was increased, in the event of AEs, according to the investigator's clinical judgment, the dose may remain the same or can be decreased by 1 dose level, to the Target dose at any time during the Treatment Period. If the dose had been decreased, it may be increased again if tolerability improves.

All subjects who complete the Core Study will be eligible to enter the Extension Phase (refer to Appendix 2 of the protocol). The last visit of the Treatment Period of the Core Study is considered to be the 1st visit of the Extension Phase.

The Follow-up Visit will be conducted 4 weeks after the last dose of study drug for subjects who do not enter the Extension Phase.

Eisai Final 4.0 Confidential Page 9 of 30

dose

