5.1.3 Other Secondary Endpoints

- Proportion of subjects who are free from convulsive seizures in the Treatment Period
- PK parameters of lorcaserin in the Treatment Period
- Safety and tolerability, including incidence of treatment-emergent adverse events (TEAEs)

5.1.4 **Exploratory Endpoints**

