5.2 Study Subjects

5.2.1 Definitions of Analysis Sets

The Safety Analysis Set is the group of subjects who received at least 1 dose of study drug and had at least 1 postdose safety assessment.

The Full Analysis Set is the group of randomized subjects who received at least 1 dose of

Eisai Final 4.0 Confidential Page 11 of 30 study drug and had at least 1 postdose primary efficacy measurement.

The PK Analysis Set is the group of all randomized subjects from whom at least measurable lorcaserin plasma concentration was obtained with associated documented dosing history.

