8.3 Definition of Visit Windows

Table 3 of the protocol presents the schedule of procedures/Assessments. The screening/baseline period is four weeks long and procedures/assessments are performed at randomization, weeks 1, 2, 4, 6, 10, and 14 of the treatment period with a follow-up of 4 weeks after end of treatment. Table 3 presents the protocol specified visits/weeks and corresponding time windows used for visit-wise analyses are presented in terms of days relative to the randomization. If more than one measurement is included in a visit window, the measurement collected closest to the scheduled date will be used in the analysis. In the case where two measurements were collected an equal number of days before and after the Scheduled Day the later of the two measurements will be used for analysis. For ECHO assessments when assessing a new or worsened event then the most severe assessment will be selected if 2 or more assessments fall within a visit window

Eisai Final 4.0 Confidential Page 23 of 30

Table 3 Visit Windows Measurements

Scheduled	Scheduled Week	Scheduled	Time Window (Days)	
1	Screening		First day of Screening	-1
2	Baseline/ Randomization	1	1	
3	1	7	2	10
4	2	14	11	17
5	4	28	18	34
6	6	42	35	48
7	10	70	49	82
8	14	98	83	101
Extension Phase				
9	15	105	102	110
10	17	119	111	125
11	20	140	126	149
12	23	161	150	169
13	26	182	170	194

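### SAP 8.1 codes seizure freedom from whatever diary days exist, so a short or very sparse diary with no recorded seizure counts as freedom over the 14-week Treatment Period

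*SAP*

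**What the plan says.** The endpoint in SAP 5.1.3 is "Proportion of subjects who are free from convulsive seizures in the Treatment Period". SAP 3.2 gives the length of that period: subjects "will receive lorcaserin or placebo for 14 weeks".

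SAP 8.1 derives it in two steps. Treatment Period frequency is the "number of seizures from the date of randomization to the end of the treatment period divided by the number of non-missing days", scaled to 28 days. The flag is then read from the percent change: "Seizure-freedom = 1 if percent change from baseline = -100" percent, and 0 otherwise. Freedom for convulsive, non-convulsive and total seizures "will be defined two ways; 1) counting seizures only and not counting clusters and 2) counting both seizures and clusters".

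The Full Analysis Set (SAP 5.2.1) asks only that a randomized subject received at least one dose of "study drug and had at least 1 postdose primary efficacy measurement". Protocol 9.5.1.2.1 asks for a daily diary, reviewed at every visit. Its only stated response to three or more consecutive missed entries is counselling.

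Multiple imputation is planned for the primary endpoint (SAP 5.3.4), and SAP Table 2 extends it to the key secondary endpoint. SAP Section 7 then drops sensitivity analysis and states that "only descriptive statistics for primary, secondary, and selected exploratory endpoints will be provided".

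**The concern.** Scaling to 28 days suits a frequency, because it adjusts a count for the time observed. Freedom is a statement about the whole period. Zero divided by any number of days is zero, so the scaling corrects nothing, and a week of diary earns the same code as 14 weeks. For a subject with a short or very sparse record, the flag does not measure the endpoint named in SAP 5.1.3.

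Short records are foreseeable. Subjects may leave the study at any time, and protocol 9.5.5 lists sponsor termination among the reasons for discontinuation. That has now happened. What is at stake is the reported seizure-free proportion in each arm, a figure that readers tend to take at face value.

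**Working it through.** The documents give no figure for seizure freedom or diary completeness, so there is none to reproduce. The enrolment figure in SAP Section 7 does check: 22/62 = 35.5%, against the stated 35%.

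**1. What the rule returns.** Let B be the baseline frequency, which is above zero for convulsive seizures because inclusion criterion 3 requires at least 4 in the 4-week Prerandomization Phase.
- 7 recorded days, no seizure, 91 days missing: 0/7 × 28 = 0; percent change = 100 × (0 − B)/B = −100%; flag = 1.
- 98 recorded days, no seizure: 0/98 × 28 = 0; percent change = −100%; flag = 1.

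The two subjects get the same code.

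**2. Whether another provision prevents this.** SAP 8.1, the analysis-set definition, the missing-data section, the estimand table and Section 7 contain no completion or minimum-days condition for this flag.

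**3. How easily a short diary gives a flag (illustration).** Assumptions: seizures follow a constant-rate Poisson process at r per 28 days, with no drug effect. The chance of none in T recorded days is P0 = exp(−r × T/28). The value r = 4 matches the eligibility count; r = 12 is an assumed comparison.

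| Recorded days T | r = 4 | r = 12 |
|---|---|---|
| 3 | exp(−0.429) = 65% | exp(−1.286) = 28% |
| 7 | exp(−1) = 37% | exp(−3) = 5.0% |
| 14 | exp(−2) = 14% | exp(−6) = 0.25% |
| 28 | exp(−4) = 1.8% | exp(−12) = 0.0006% |
| 98 | exp(−14) = 0.00008% | effectively 0 |

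P0 falls below 1% once T exceeds 28 × ln(100)/r, which is 32.2 days at r = 4 and 10.7 days at r = 12. Under this model the problem lies in short or very sparse diaries.

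**4. Weight of one subject.** Assuming 11 per arm, one subject is 1/11 = 9.1 percentage points. For arms of 13 or 9 it is 7.7 or 11.1 points.

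**5. Rough expected count.** Suppose the 12% planning dropout in SAP Section 4 applied to truncated diaries: 0.12 × 22 = 2.64 subjects. If stopping days were uniform over 98 days, the mean of P0 is about (28/r)/98, which is 0.071 at r = 4 and 0.024 at r = 12. That gives about 0.2 and 0.06 spurious flags in both arms together. If all stopped on Day 7, it gives 2.64 × 0.368 = 1.0 and 2.64 × 0.050 = 0.13. The 12% may instead mean loss from the Full Analysis Set, so this shows scale only.

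**The case against.** **Weight.** This is an other secondary endpoint outside the gatekeeping sequence, now reported descriptively for 22 subjects. The 9.1 points per subject would hold for any proportion with 11 in the denominator. Under the assumptions in step 5, the expected number of spurious flags is about one or fewer. All of this stands and limits the consequence. It does not make the flag correct for the subjects it misclassifies.

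**The observed-days approach is deliberate.** It is used uniformly for the primary endpoint, 50% response and freedom. That is a good reason to leave the response rule alone and to keep the observed-days figure in view. It is not a reason to read freedom over 14 weeks from a few days.

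**Unseen documents.** SAP Sections 9 and 11 place derivation rules and table shells elsewhere, so a coverage rule may exist there. If so, SAP 8.1 should state or cite it.

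Four stronger readings are tempting, and the documents do not support them:
- *That diaries end when study drug ends.* In protocol Table 3, as extracted, the early discontinuation visit retrieves the diary without dispensing another. Protocol 9.3.3 sends a subject who stops treatment into follow-up. However, it also says that one who stops drug but stays in the study continues on the regular schedule, which dispenses diaries. The exposure is mainly subjects who leave the study or record little. SAP 8.1 does not say whether off-drug days up to Week 14 count.
- *That r = 4 is the worst case.* Four is a minimum observed baseline count and not a minimum true rate. A lower true rate, or clustering of seizures, would raise the chances shown, so they are not bounds.
- *That the rule inflates the lorcaserin rate or favours one arm.* The documents give no rate of short diaries by arm, so the direction is unknown.
- *That the Visit 8 window (Days 83 to 101) supplies a completion rule.* SAP 8.3 says that its "corresponding time windows used for visit-wise analyses are presented in terms of days relative to the randomization". It was not written to define completion.

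**Conclusion.** The point holds in a limited form. As printed, SAP 8.1 gives a wrong value of the stated endpoint for any subject with no recorded convulsive seizure and an early-ending or very sparse diary. This is a stated rule with a faulty result, and not merely a missing detail.

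The consequence is confined to one descriptive proportion. No hypothesis test or error rate depends on it. The number of subjects affected cannot be derived from the documents. The percentages rest on the Poisson, no-drug-effect and rate assumptions, and the per-subject shift on the assumed arm size. The convulsive-seizure figures do not carry over to non-convulsive seizures, for which the protocol sets no baseline minimum. The change is worth making because it is cheap and the proportion will still be reported.

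**What to change.** In SAP 8.1, code convulsive seizure freedom as 1 only if all three conditions hold:
1. no convulsive seizure is recorded from randomization to the end of the 14-week Treatment Period;
2. the subject has diary data through the Week 14 visit, on or off study drug;
3. diary coverage over that time meets a minimum share that the sponsor fixes before database lock.

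Otherwise code 0, with all Full Analysis Set subjects in the denominator. Beside this proportion, show by arm:
- the observed-days proportion as now defined;
- the number of subjects with no recorded seizure but an incomplete record, identifying those cut short by sponsor termination;
- recorded Treatment Period days.

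Apply the same rule to both cluster versions, and to any non-convulsive or total seizure-freedom output that is reported. Leave the 50% responder rule unchanged. A subject with a short record could then be a responder at −100% and not be coded free; a footnote should explain that one is a rate and the other a statement about the whole period.

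Cost: a few lines of SAP text, one derived flag and a few descriptive rows, with no new data. Downside: a subject who was truly free until early withdrawal, or until the sponsor stopped the study, counts as not free, so the proportion may be lower. The companion figures let the reader see by how much.
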